9.6.3 Secondary Endpoints

Secondary efficacy endpoints will be analyzed using the FAS and the PP analysis set, whereas secondary safety endpoints will be reported using the safety analysis set.

The time from randomization to the first occurrence of a daily volume of MoM ≥ 500 mL and ≥ 750 mL will be analyzed by fitting a discrete time survival model adjusted for gestational age group, as well as the baseline volume of MoM.

The proportion of maternal subjects producing at least 500 mL and 750 mL of MoM over Days 1 to 14 will be analyzed by repeated logistic regression adjusted for treatment day, treatment-by-day interaction and gestational age group.

The volume of MoM produced over Days 15 to 17 will be compared between treatment groups using a repeated measures ANCOVA model adjusting for the volume of MoM produced on Day 14.

Volume of MoM fed to the infant over Days 1 to 14 and volume of formula/donor milk fed to the infant over Days 1 to 14 will be analyzed and presented using an ANCOVA approach similar to the one used for the primary endpoint but gestational age will be adjusted for as a continuous covariate.

The proportion of subjects with quantifiable amount of merotocin in the milk will be summarized for the merotocin group.

Infant body weight will be summarized by treatment day, treatment group and gestational age measured in weeks, together with change from baseline values.

Maternal subject TEAEs will be summarized by treatment group, including separate summaries by intensity. All infant AEs will be summarized by treatment group, again including separate summaries by intensity. Further details are provided in Section 9.8.2.

Routine safety laboratory parameters of maternal subjects will be summarized by time point and treatment group, together with change from baseline values. For each laboratory parameter, a summary table will be prepared displaying the proportion of maternal subjects who have at least one markedly abnormal value. Markedly abnormal criteria for the safety laboratory parameters will

be specified in the SAP.

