3.6 Discussion of Overall Trial Design and Choice of Control Groups

3.6.1 Trial Design

This trial will investigate the efficacy and safety of repeated intra-nasal administrations of merotocin compared to placebo in increasing milk production in women with preterm delivery and inadequate initial milk production.

The trial design employs best practices for establishing an adequate milk supply. All maternal subjects will institute a high frequency milk expression regimen and will receive standardized lactation counselling and ongoing support consistent with guidelines for promoting lactation in this population.

There is no approved product for women with lactation deficiency in the country where the trial will be conducted. Some pharmacologic agents are used in clinical practice to increase milk supply, but there is only limited medical evidence to support the safety and efficacy of the use of these agents to correct lactation deficiency in women with preterm delivery.^{25,26,27} For these reasons, a placebo comparator is necessary to evaluate the potential of merotocin to increase milk production in this population.

The window for randomization, originally set to 96 to 144 hours of delivery, was chosen to enhance the probability of selecting maternal subjects who truly have an inadequate milk supply but also to ensure that intervention is instituted early enough in the postpartum period to have an impact. By the amendment (dated 06-04-2022), the window was expanded to 96 to 192 (+4) hours of delivery to allow adequate time for the maternal subjects to appreciate and understand the value of participating in the trial, with a negligible risk for any negative impact on induction of lactation. Allowing randomization earlier in the postpartum period might select maternal subjects, whose milk supply appears inadequate due to delayed onset of lactogenesis II but who may ultimately establish an adequate milk supply without intervention.

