3.6.2 Selection of Endpoints

The primary endpoint for this trial is volume of MoM produced over Days 1 to 14. The volume of MoM produced for each treatment day will be recorded and derived for each subject. These daily volumes of MoM produced will be analyzed using a repeated measures analysis of covariance (ANCOVA) to allow for investigation of the overall treatment effect in the primary analysis and the onset of treatment effect of merotocin compared to placebo in supportive analyses.

The secondary endpoints (Section 2.2) will provide further evaluation of the milk volume produced over Days 1 to 14. The recommendation for a lactating mother of a non-nursing preterm infant is to establish an adequate milk supply, defined as a daily milk volume of ≥ 500 mL, during the first two weeks after delivery. Evidence suggested that adequate milk production at 1-2 weeks postpartum, particularly 1 week postpartum, is highly predictive of milk adequacy at 6 weeks postpartum.¹ Therefore it is clinically relevant to assess the time it takes for maternal subjects to reach the target daily milk volume of ≥ 500 mL or a more ambitious goal of ≥ 750 mL. Striving for reaching these targets sooner than later may also motivate mothers to continue milk expression on a regular basis. For the same purpose, an additional secondary endpoint, an assessment of the proportion of women with an ‘adequate milk supply’ over Days 1 to 14 is also included.

The secondary endpoints will also examine whether any observed treatment effect of merotocin is maintained over the three days after discontinuation of treatment. The infant body weight is a standard growth parameter to indicate that the infant is growing and developing as expected. The safety assessments selected are standard for the maternal subjects.

The effect of merotocin on milk composition as well as the relationship between merotocin exposure and milk volume will be explored.

For the post-trial endpoint related to time to tolerance of full enteral feed, 150 mL/kg/day is used to define full enteral feed in order to standardize the assessment.^{28,29} For the long-term follow-up of infants, the administration of ASQ-3 has been recommended by both FDA and American Academy of Pediatrics to screen child developmental disorders.

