9 STATISTICAL METHODS

The Ferring Global Biometrics Department will be responsible for the statistical analyses of the primary, secondary and exploratory endpoints. This section details the planned statistical analyses for the primary endpoint and outlines the planned statistical analyses for the secondary and exploratory endpoints. All analyses and further descriptions of the statistical methodology for the primary, secondary and exploratory endpoints will be included in the Statistical Analysis Plan (SAP) available before breaking the blind of the trial. A separate SAP will be prepared to cover the post-trial information.

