9.6.2 Primary Endpoint

Primary Endpoint: Primary Analysis

The primary objective of this PoC trial is to evaluate the effect of merotocin on increasing milk production in women with preterm delivery. The primary endpoint of the trial is the volume of MoM produced over Days 1 to 14.

Repeated Measures ANCOVA Model:

The primary endpoint will be analyzed using a repeated measures ANCOVA with a general (unstructured) covariance matrix. The daily volume of MoM produced will be the dependent

variable. The model will include the baseline volume of MoM produced as covariate, with treatment group, treatment day, treatment-by-day interaction, and gestational age group (<27 weeks and \geq 27 weeks) as factors. The baseline volume of MoM produced is defined as the volume obtained at the 24-hour interval for eligibility during the observation period. The average treatment effect across treatment days and the within-day treatment effect will be reported along with the corresponding two-sided 95% confidence intervals and p-values.

The analyses based on the FAS will be considered the primary, while the analyses based on the PP analysis set will be considered supportive. PoC will be considered to be established if the repeated measures ANCOVA model results in a significant positive average treatment effect of merotocin compared to placebo across the treatment period in the FAS.

Primary Endpoint: Sensitivity/Supportive Analyses

The Safety Committee may choose to reduce the dose in case of any safety concerns. In that case, the analyses will be performed both by combining the merotocin dose groups into one and by using the actual merotocin dose groups separately.

Sensitivity analyses exploring the impact of the missing data assumption on the results of the primary analysis will be performed for the FAS and PP analysis sets. Missing data will be imputed under a MNAR assumption using the pattern-mixture model with control-based pattern imputation.

The sensitivity of the results with respect to choice of the covariance structure will be investigated using more restrictive covariance structures (compound symmetry, Toeplitz, separate compound symmetry for each treatment group, and separate Toeplitz pattern for each treatment group). Nested models will be compared using the likelihood ratio test. In addition, interactions of treatment and gestational age group will be tested in the model with a general covariance structure.

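### The repeated logistic model for women reaching 500 and 750 mL leaves out baseline milk volume, unlike the time-to-threshold and primary models, and loses power to the extent that baseline predicts later volume

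*Combined protocol and SAP*

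**What the plan says.** Section 9.6.3 names the terms of the repeated logistic model for the 500 and 750 mL proportions: the analysis "will be analyzed by repeated logistic regression adjusted for treatment day, treatment-by-day interaction and gestational age group". The treatment main effect is implied by the interaction. Baseline volume is neither named nor implied.

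The other milk-volume analyses read as follows:

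- **Time to 500 and 750 mL (9.6.3):** "fitting a discrete time survival model adjusted for gestational age group, as well as the baseline volume of MoM".
- **Primary analysis (9.6.2):** "The model will include the baseline volume of MoM produced as covariate".
- **Volume over Days 15 to 17 (9.6.3):** "using a repeated measures ANCOVA model adjusting for the volume of MoM produced on Day 14".
- **Volumes of own milk and of formula or donor milk fed to the infant (9.6.3):** "analyzed and presented using an ANCOVA approach similar to the one used for the primary endpoint", with gestational age as a continuous covariate.

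Section 9 says that the protocol only "outlines the planned statistical analyses for the secondary and exploratory endpoints", and that a separate SAP, due before the blind is broken, will describe the methods further. That SAP is not part of the supplied text.

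**The concern.** Two analyses of the same threshold data would adjust for different things, and the plan does not say why. Elsewhere it does explain a left-out term: Section 9.6.2 gives its reasons for omitting site from the primary model. Here there is silence, which looks like an oversight.

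At stake is precision, not validity. The proportion at 500 mL or more is the plan's own measure of adequate supply (Section 3.6.2). With about 100 women and an assumed 30% drop-out, an informative covariate that is already collected is worth using. If baseline predicts later volume, the logistic model will be less likely than it could be to detect a real effect.

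**Working it through.** **1. The plan's own figures.** No power is stated for this endpoint. The nearest figure is 80.2% for the primary analysis (Section 9.1, Table 7: 50% increase, within-woman correlation 0.8). It cannot be reproduced, because the means and variances come from external data that are not shown. It can be used to gauge the spread:

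- The SD of a woman's 14-day log mean is SD × √((1 + 13ρ)/14). At ρ = 0.8 this is SD × √(11.4/14) = 0.902 × SD.
- With 50 per arm and a difference of ln 1.5 = 0.405, power of 80.2% needs a log-SD of 0.80.
- That SD gives 84.7% against a stated 86.1% (ρ = 0.7) and 89.2% against 92.3% (ρ = 0.6). At a 30% increase it is up to 10 points low. Table 7 comes from a simulation that is not fully specified, so this is not evidence of an error.
- The CVs assumed below, 0.75 and 1.0, correspond to log-SDs of √ln(1 + 0.75²) = 0.67 and √ln 2 = 0.83, which bracket 0.80.

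**2. Inputs to the simulation.**

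- *From the protocol:* 50 women per arm, 50% increase, within-woman correlation 0.6 or 0.8, uniform 30% drop-out (9.1), baseline under 200 mL (4.1.1, criterion 11), two-sided 5% test (9.6.1).
- *Assumed:* placebo mean rising linearly over Days 1 to 14 from 150 to 300, 200 to 450 or 250 to 600 mL; CV 0.75 or 1.0; log-normal volumes; baseline log-normal with mean 150 mL before truncation at 200 mL; 20% of women below 27 weeks; correlation r of log baseline with log daily volume among randomized women of 0, 0.15, 0.3, 0.5 or 0.7.
- This gives 3 × 2 × 2 × 5 = 60 scenarios, each run with the effect and with no effect, 2,000 trials per cell.

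**3. Model.** logit P(volume ≥ threshold) = treatment + day + day² + treatment × day + gestational age group, with and without baseline in mL. The fit uses independence working correlation and cluster-robust standard errors. The test is of the log odds ratio averaged over Days 1 to 14. Fits that did not converge count as non-significant.

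**4. Change in power from adding baseline, in percentage points (12 scenarios per cell).**

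| r | 500 mL | 500 mL, size-matched | 750 mL | 750 mL, size-matched |
|---|---|---|---|---|
| 0 | -1 to 0 | -2 to 2 | -1 to 0 | -1 to 1 |
| 0.15 | -1 to 1 | -2 to 2 | 0 to 1 | -1 to 2 |
| 0.3 | 1 to 5 | 1 to 6 | 1 to 4 | -1 to 4 |
| 0.5 | 6 to 12 | 4 to 12 | 1 to 10 | 0 to 10 |
| 0.7 | 6 to 25 | 7 to 23 | 4 to 21 | 3 to 21 |

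Size-matched columns use critical values taken from the matching no-effect runs. Type I error was similar without and with baseline: 3.8-8.6% against 3.6-8.5% at 500 mL, and 4.9-13.0% against 4.7-12.4% at 750 mL. The high values come mainly from slow-growth scenarios with few events and affect both models alike.

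**5. Cross-checks at 500 mL.**

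- Day as a 14-level factor with interaction (fast growth, ρ = 0.8, 1,000 trials), size-matched: -1 to 3 points at r = 0, 0 to 6 at 0.3, 7 to 12 at 0.5, 10 to 19 at 0.7.
- A simpler simulation with no entry limit (log-SD 0.75, 20% or 40% of placebo women at 500 mL or more each day, linear day, 600 trials): about 0 points at r = 0, 3 to 4 at 0.3, 9 to 16 at 0.5, 16 to 26 at 0.7. For example, at ρ = 0.8 and 20%, r = 0.3 takes power from 68.8% to 73.2%.
- A further run (CV 0.75, ρ = 0.8, 600 trials): 0 to 2 points at r = 0, 1 to 4 at 0.3, 7 to 10 at 0.5, with type I error near 5% both ways.

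**6. Which r is plausible.** The entry limit truncates baseline and shrinks its correlation to r√k / √(1 - r²(1 - k)), where k is the truncated-to-full variance ratio of log baseline. For an untruncated mean of 100-250 mL and CV 0.75-1.0, k is 0.36-0.74. For r = 0.5 and k = 0.36: 0.5 × 0.6 / √(1 - 0.25 × 0.64) = 0.30/0.917 = 0.33; with k = 0.74 the result is 0.44. In the same way, 0.3 becomes 0.19-0.26 and 0.7 becomes 0.51-0.64. Having r = 0.7 among randomized women would therefore need an untruncated value above 0.7.

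**The case against.** **The text is only an outline.** Section 9 defers detail to the SAP, and the sentence is shorthand that does not even name the treatment effect. This stands as a limit: the SAP may add the term. But the protocol gives an explicit covariate list, and a SAP author who follows it will leave baseline out.

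**The wider pattern is thinner than it looks.** The Days 15 to 17 model conditions on a post-randomization volume, and the fed-volume models are only said to resemble the primary one. This is correct. The firm contrast is with the two models that name baseline.

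**The protocol gives little evidence that baseline predicts.** Section 3.6.2 says adequate production early on, "particularly 1 week postpartum, is highly predictive of milk adequacy at 6 weeks postpartum", and baseline here is measured at about Days 4 to 8 (96/24 to 192/24). But adequacy there means 500 mL or more, and every randomized woman is below 200 mL, so the statement says little about prediction within that range. Section 3.6.1 also describes women "whose milk supply appears inadequate due to delayed onset of lactogenesis II but who may ultimately establish an adequate milk supply without intervention", although the 96-hour floor is meant to limit their number. These points stand, and they are why the claim is conditional.

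**The 750 mL figures are fragile.** If day enters as a 14-level factor, any arm-by-day cell with no events prevents finite estimates. With the 50% increase, at least one such cell occurred at 750 mL in 19-48% of trials (fast growth), 55-89% (middle) and 92-100% (slow); at 500 mL with slow growth it was 41-77%. This stands: the 750 mL gains deserve little weight if day is a factor.

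**It is only an efficiency preference.** The secondary endpoints have no multiplicity control and are to be read cautiously (9.6.1), and the unadjusted test is valid. That limits the importance, but it does not explain why the two threshold models differ.

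**Conclusion.** The concern holds as a minor one. The logistic model as written omits baseline volume, while the time-to-threshold model for the same cut-offs and the primary model include it, and no reason is stated.

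Under randomization with ordinary drop-out, this brings no bias and no material change in type I error. The cost is power, conditional on a correlation that the protocol does not give. At 500 mL the change from adding baseline is about nil if baseline is uninformative, 1 to 5 points at a correlation of 0.3 and 6 to 12 points at 0.5. The larger gains at 0.7 should carry little weight. All figures depend on the assumed growth curves, CVs and correlations. The proof-of-concept decision is unaffected.

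**What to change.** In the SAP, before unblinding, add baseline milk volume as a single continuous covariate to the repeated logistic model and keep the treatment-by-day interaction; or state why baseline is omitted. It would help to say at the same time whether day is a factor or a trend, given the empty cells expected at 750 mL.

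The cost is wording only: the e-CRF already calculates the baseline volume for eligibility (Section 4.2.2). If baseline proves uninformative, the loss is at most about 1 point, or 2 when size-matched. One small side effect should be handled: the odds ratio becomes conditional on baseline. In the simpler simulation at r = 0.5, the median log odds ratio moved from about 0.9 to 1.0-1.1. The SAP should name the odds ratio it targets, and a standardized risk difference can be reported beside it.

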2 TRIAL OBJECTIVES AND ENDPOINTS

2.1 Objectives

Primary Objective

- To evaluate the effect of merotocin on increasing milk production in women with preterm delivery and with inadequate milk production

Secondary Objectives

- To evaluate the effect of merotocin on milk production after treatment discontinuation
- To evaluate the amount of mother's own milk (MoM) in the infant enteral nutritional intake and changes in infant body weight
- To evaluate any amount of merotocin from maternal plasma into the milk expressed by women with preterm delivery exposed to merotocin
- To characterize the safety profile of merotocin in women with preterm delivery and their infants

Exploratory Objectives

- To explore the relationship between merotocin exposure in maternal plasma and milk volume
- To evaluate composition of milk produced during treatment with merotocin in women with preterm delivery

Post-trial Objectives

- To explore post-trial feeding patterns and key parameters of neonatal intensive care unit (NICU) hospitalization of infants from women with preterm delivery and inadequate milk production
- To assess the post-trial long-term development of infants from women with preterm delivery and inadequate milk production

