Breastfeeding will only occur when the trial center staff consider the infant has the ability to achieve a nutritional feed through breastfeeding. It is expected that the infant will be hospitalized for the predominant or entire duration of the trial due to their prematurity. Should breastfeeding occur, the amount of breastfed milk is established by weighing the infant before and after the breastfeeding has been completed by following standardized weighing instructions and by using a standardized scale.²⁴ The weights before and after breastfeeding will be recorded with assistance from the NICU staff, if breastfeeding occurs at NICU. If the infant is discharged to home prior to the Day 18/Follow-up visit, the maternal subject will be provided with a standardized scale to use at home for measuring the weight of the infant before and after feeding and will record the required information for each breastfeeding session in accordance with instructions provided in the lactation

manual for subjects. After breastfeeding her infant, the maternal subject should continue to express milk using the breast pump.

The milk volume collected on each day from Days 1 to 14, including any amount given to the infant by breastfeeding, will be calculated as the total production in each treatment day. In this trial, treatment days start from the time of randomization, with Day 1 being the first 24 hours after randomization, Day 2 being 24 to 48 hours after randomization and so on. For example, if a subject is randomized at 10 AM, her first treatment day or Day 1 is from 10 AM on that day to 10 AM on the next day. The treatment period will include 14 such consecutive intervals of 24 hours from the time of randomization, corresponding to 14 treatment days (Days 1 to 14). Trial visits can be scheduled according to calendar days without considering 24-hour periods.

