7.2 Assessments Related to Secondary Endpoints

7.2.1 Time to the First Occurrence of a Daily Volume of MoM \geq 500 mL and \geq 750 mL

The volume of MoM produced on each treatment day will be calculated by using recorded weights of expressed milk in the same method as described in Section 7.1.1. The time from randomization to the first treatment day when maternal subjects produce a daily volume of MoM \geq 500 mL and \geq 750 mL will be calculated.

7.2.2 Proportion of Subjects with a Daily Volume of MoM \geq 500 mL and \geq 750 mL

The volume of MoM produced on each treatment day will be calculated by using recorded weights of expressed milk in the same method as described in Section 7.1.1. The proportion of maternal subjects who produce a daily volume of MoM \geq 500 mL and \geq 750 mL will be calculated for every treatment day from Days 1 to 14.

7.2.3 Volume of MoM Produced over Days 15 to 17

Maternal subjects who complete Days 1 to 14 of assigned treatment will be asked to continue recordings of milk expression on milk container labels through the end of Day 17. The volume of MoM produced over Days 15 to 17 will be calculated by using recorded weights of expressed milk in the same way as described in Section 7.1.1.

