on any two given days by the same individual was assumed to be constant and is provided in [Table 7](#) for each scenario. To account for subjects not completing the trial, a 30% drop-out rate over the duration of the trial was built into each simulation. It is estimated that approximately 250 maternal subjects will need to be screened.

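### The Days 15-17 comparison adjusts for Day 14 volume, an on-treatment value, so a fully maintained effect is shrunk by about 60-80% and a lost effect can look like harm.

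*Combined protocol and SAP*

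**What the plan says.** The first secondary objective in section 2.1 reads "To evaluate the effect of merotocin on milk production after treatment discontinuation". Section 3.6.2 gives the reason for the endpoint: to see "whether any observed treatment effect of merotocin is maintained over the three days after discontinuation of treatment".

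For the analysis, section 9.6.3 compares Days 15-17 volume between groups "using a repeated measures ANCOVA model adjusting for the volume of MoM produced on Day 14". It mentions neither the pre-randomization volume nor gestational age group for this endpoint.

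Section 7.1.1 counts days in 24-hour intervals from randomization, "corresponding to 14 treatment days (Days 1 to 14"), so Day 14 is an on-treatment day. By contrast, the primary model in section 9.6.2 adjusts for a pre-treatment value: "The baseline volume of MoM produced is defined as the volume obtained at the 24-hour interval for eligibility during the observation period".

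Section 7.2.3 limits who supplies the data: "Maternal subjects who complete Days 1 to 14 of assigned treatment will be asked to continue recordings of milk expression" through Day 17. The opening of section 9 leaves further description to a SAP, which is not among the documents reviewed, and section 9.6.1 adds descriptive summaries. No Days 15-17 comparison without the Day 14 term is described.

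**The concern.** Adjusting for a variable that treatment has already changed removes part of the effect one wants to estimate. Here the covariate is the same outcome one to three days earlier, so most of a persisting effect would be absorbed.

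Two questions are put to this endpoint, and the model answers neither cleanly:

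- **Effect after discontinuation.** The target is the plain difference between randomized groups over Days 15-17. The model reports something smaller, and possibly of the opposite sign.
- **Maintenance.** A test of maintenance should be centred on zero when the whole effect is kept. This one is centred on a positive value then, and on zero only when a sizeable part has been lost.

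At stake is the only inferential analysis described for this objective. Women on merotocin could still be producing more milk than women on placebo while the report shows a null or significantly negative difference, which could be read as a rebound after stopping.

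**Working it through.** **The plan's own figures.** The documents give no power or precision for Days 15-17. Table 7 (section 9.1) is the nearest figure, but its means and variances come from undisclosed external data, so it cannot be rebuilt. As a calibration, take the 14-day average with variance factor (1 + 13ρ)/14 and 30% drop-out. The 80.2% cell (ρ = 0.8, 50% increase) then implies a standardized effect of about 0.51. The same effect predicts about 84.5% at ρ = 0.7 (86.1% stated) and about 89% at ρ = 0.6 (92.3% stated). That is similar in direction and size, and no error is inferred.

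**Inputs**

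- Within-subject correlation ρ of 0.6 to 0.8, constant between any two days: section 9.1. Applying it to Day 14 versus Days 15-17 is an extension.
- Effect on Day 14: 50% multiplicative increase, the planning effect.
- Completers: "a 30% drop-out rate over the duration of the trial was built into each simulation", so 100 × 0.7 = 70, or 35 per arm.
- Log-normal volumes as in section 9.1. The coefficient of variation (CV) is an assumption: 0.75, range 0.5 to 1.0. A 50% multiplicative effect gives a pooled SD of 0.75 × √((1 + 2.25)/2) = 0.956 placebo means, so the standardized effect is 0.50/0.956 = 0.52, close to the 0.51 implied by Table 7.

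**Identity.** With Day 14 as covariate, the treatment coefficient is

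estimate = d(15-17) − b × d(14),

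where d is the difference between groups and b the pooled within-group slope. With equal SDs, b = ρ. A share k of the Day 14 effect still present then gives (k − ρ) × d(14): 40% or 20% of the effect at k = 1, and −60% or −80% at k = 0.

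**Unequal SDs.** A multiplicative effect makes the treated SD 1.5 times the placebo SD on Day 14 and (1 + 0.5k) times afterwards, so

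b = ρ × [1 + 1.5 × (1 + 0.5k)] / 3.25.

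This is ρ at k = 1, 0.88ρ at k = 0.5 and 0.77ρ at k = 0. The estimate, in placebo means, is 0.5k − 0.5b.

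**Results.** Simulation used 3,000 trials per scenario, 35 per arm, and ANCOVA on the mean of Days 15-17. Percentages are for CV 0.75, with the range over CV 0.5 to 1.0 in brackets. Estimates hardly change with CV.

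| Share kept (true difference) | ρ | b | Closed form | Simulated | Significance, two-sided 5% |
|---|---|---|---|---|---|
| All (+0.50) | 0.6 | 0.60 | +0.20 | +0.19 | power 27% [17-50]; without Day 14, 74% [51-97] |
| All (+0.50) | 0.8 | 0.80 | +0.10 | +0.09 | power 14% [8-24]; without Day 14, 68% [45-95] |
| Half (+0.25) | 0.6 | 0.53 | −0.02 | −0.02 | significantly negative 4% [3-4] |
| Half (+0.25) | 0.8 | 0.71 | −0.10 | −0.11 | significantly negative 20% [15-33] |
| None (0) | 0.6 | 0.46 | −0.23 | −0.23 | significantly negative 53% [39-81] |
| None (0) | 0.8 | 0.62 | −0.31 | −0.31 | significantly negative 93% [79-100] |

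**Where the estimate crosses zero.** Setting k = b gives k = 2.5ρ / (3.25 − 0.75ρ): 1.5/2.80 = 0.54 at ρ = 0.6 and 2.0/2.65 = 0.75 at ρ = 0.8. Below these shares the expected estimate is negative although the true difference is still positive.

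**Sensitivity.** If ρ is taken on the log scale, shrinkage of a maintained effect is about 53% to 78%.

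**The case against.** The best defence is that Day 14 was chosen deliberately as the reference for maintenance. Read that way, a negative estimate after partial or full loss points in the right direction. Day 14 also adjoins Days 15-17, so the correlation may exceed 0.8. At ρ = 0.9 and 0.95 a fully maintained effect is estimated at only +0.05 and +0.02, with about 8% and 6% of trials significant, and full loss is detected in over 99%. That is close to a valid maintenance test.

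This narrows the maintenance criticism but does not remove it within the plan's own range, where 14% to 27% of trials are significant under full maintenance. A higher correlation also makes the stated objective worse served: at ρ = 0.9 with equal SDs, 90% of the post-treatment effect is removed.

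Second, section 9 only outlines the secondary analyses, and the SAP might add the baseline volume. The text does not say so. If it did, with equal SDs and a baseline correlation equal to ρ, the slope would be ρ/(1 + ρ), which is 0.375 to 0.444, so shrinkage would still be about 38% to 44%. With weaker baseline correlations of 0.3 to 0.5 it is about 50% to 79%. At ρ = 0.6 and baseline correlation 0.5, a half-kept effect would no longer be negative (+0.035). So 60-80% holds only for the model as written.

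Third, this is one secondary endpoint in a proof-of-concept trial, with no multiplicity control and cautious interpretation promised (section 9.6.1). Group means and the Day 14 effect will also be reported, so a careful reader could see that the merotocin group still produced more milk. That limits the harm, but it does not make the planned confidence interval and p-value correct.

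**Conclusion.** The concern holds. As written, the Days 15-17 model does not estimate the effect after discontinuation, and it is a biased test of maintenance. The direction follows from algebra: with any positive Day 14 effect and a positive slope, the estimate lies below the true Days 15-17 difference.

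The 60-80% shrinkage of a fully maintained effect rests on the plan's correlations of 0.6 to 0.8 carrying over to Day 14 versus Days 15-17, and on Day 14 being the only covariate. For a fully lost effect, the downward bias is 60-80% of the Day 14 effect with equal variances, and about 46-62% under a multiplicative effect. The power figures also depend on the assumed CV and on 35 completers per arm, so they are illustrative.

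This should be corrected before unblinding. The primary analysis and the proof-of-concept decision are not touched.

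**What to change.** Remove Day 14 volume as a covariate. Extend the primary repeated measures model (pre-randomization 24-hour volume, gestational age group, treatment, day, treatment-by-day) to Days 1-17, then report from that one model, each with a 95% confidence interval:

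1. the treatment difference averaged over Days 15-17, as the effect after discontinuation;
2. that average minus the Day 14 difference, as the measure of maintenance.

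The unstructured matrix grows from 14 × 15/2 = 105 to 17 × 18/2 = 153 parameters, with only about 70 completers if drop-out is 30%, so non-convergence is a real possibility. Pre-specify a fallback: Days 14-17 fitted jointly as outcomes (4 × 5/2 = 10 parameters) with the same baseline terms. The Day 14-adjusted model may stay as a labelled descriptive supplement.

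In simulation (2,000 trials per scenario, CV 0.75, assumed log-scale baseline correlation 0.3 to 0.5):

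- The maintenance contrast averages 0.00 under full maintenance, with 4-6% of trials significant, and −0.50 under full loss, with 89-99% significant.
- The baseline-adjusted Days 15-17 difference is unbiased, with 71-86% power for a maintained effect.

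**Cost.** No new data are needed. The model is written in the protocol, so section 12.1 calls for an amendment as well as SAP wording. The Days 15-17 difference is less precise than an estimate conditioned on Day 14, and power for a half-kept effect is only 28-40%. Only treatment completers are asked to record Days 15-17, and the report should say so. The Days 1-17 model uses the earlier data of women who stop, but it does not by itself remove selection by drop-out.
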